The study will only be initiated after it has completed review and approval by the Mayo Institutional Review Board (the IRB). Scientific review will initially be conducted by the Endocrine Research Unit and by the Clinical Research Trials Unit, prior to ethical approval by the IRB which will also approve all patient contact material, advertising and consent forms. The latter will be utilized to ensure informed, written consent is obtained at the time of screening where they will meet the principal investigator or a member of the team to ensure that participants meet entry criteria for the study, understand the risks of participation and the goals of the study.

All Mayo IRB approved studies adhere to the Declaration of Helsinki and are conducted in accordance with ICH good clinical practice (GCP) guidelines. [name] in his role as sponsor-investigator will comply with all these guidelines as well as the other applicable regulatory and legal guidelines during study conduct and when obtaining and documenting informed consent.

The nature of the information obtained for the purposes of the study will be explained in detail to each participant at the time of screening. Specifically, none of this information will become part of the medical record and cannot impact the availability and nature of care or access to healthcare. All information will be stored anonymously in the database and only the PI or one of his designates will have access to the data.

Study Hypothesis: Agonism of the GLP-1 receptor by Liraglutide 3mg will increase weight loss and lower blood pressure and LDL-cholesterol compared to placebo after sleeve gastrectomy.

1° Endpoint: Liraglutide administration (3mg daily) to participants after SG produces significantly greater weight loss from baseline compared to that observed in the group after sleeve gastrectomy who receive placebo.

2° Endpoints:

[figure not shown]
- i. Liraglutide administration (3mg daily) to participants after SG produces will achieve weight loss that is inferior to that achieved by RYGB.
- ii. Greater numbers of participants after SG will have an LDL \leq 100mg/dL and a systolic blood pressure \leq 130mmHg results when receiving Liraglutide (3mg daily) compared to placebo.
- iii. Liraglutide administration (3mg daily) to participants after SG produces blood pressure and LDL-cholesterol lowering that is inferior to that achieved by RYGB.

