We propose enrolling 60 non-diabetic adults scheduled for SG and 30 patients undergoing RYGB. Patients scheduled for SG will be randomized to receive Liraglutide (3mg daily) in a double-blind, randomized, placebo-controlled fashion (randomized in a 1:1 ratio). All participants will be followed longitudinally with serial measurement of outcome variables (weight, blood pressure, lipid profile, activity and satiety) over a three year period. Our power calculations suggest that 25 patients per group will be sufficient to accomplish our goals even with a loss of 5 subjects per group to follow up.

Bariatric Sx	2008		2009		2010		2011		2012		2013	
	ND	DM										
RYGB	107	46	166	70	160	63	207	83	184	64	210	59
AGB	9	0	27	0	10	0	34	4	8	2	3	1
SG	0	0	25	0	32	10	62	29	78	25	102	36

Table 1: Total numbers of laparoscopic surgeries performed as 1st procedure at Mayo Clinic. AGB = Adjustable Gastric Banding; ND = Non-diabetic; DM = Diabetic patients.

a) Subjects: A total of 75 patients will be recruited from the Nutrition Clinic at Mayo Clinic Rochester prior to undergoing bariatric surgery. Of these 25 will be scheduled for RYGB while the remainder (50) are scheduled for SG. Healthy status will indicate that the participant has no known active systemic illnesses or active macrovascular disease. To be eligible subjects must be willing to participate in all the studies outlined. **Baseline Visit:** Subjects will provide written informed consent. To ensure they are healthy, subjects will undergo a history and physical examination including supine and standing blood pressure; blood collection for complete blood count, HbA_{1c}, fasting lipid profile, electrolytes, hepatic panel and urine collection to exclude pregnancy in females of child bearing potential. Habitual activity levels⁴¹, and bowel symptoms⁴² will be assessed.

BMI $\geq 35 \text{ kg/M}^2$ in the presence of at least one weight-related comorbid condition including hypertension, obstructive sleep apnea or dyslipidemia. Alternatively, a BMI $\geq 40 \text{ kg/M}^2$ without comorbid conditions is deemed to confer eligibility for bariatric surgery at the Mayo Clinic.

ii. Age will be between 20 and 65 years of age.

- iii. Subjects will have no active physical illness which will interfere with mobility or weight loss after bariatric surgery.

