- iv. Prior to acceptance for surgery, patients seen in the bariatric clinic must undergo psychological assessment and complete a supervised comprehensive lifestyle program. Please refer to ⁴⁶ for details.
- v. Female subjects (randomized to study drug) who are sexually active and able to become pregnant, must agree to use birth control methods for the duration of the study

c) Exclusion Criteria:

- i. Prior use of glucose lowering medication in the 3 months prior to screening.
- ii. A fasting glucose $\geq 126\text{mg/dl}$ or an HbA1c $\geq 6.5\%$ will be taken as evidence of type 2 diabetes and therefore patients will be deemed ineligible for participation.
- iii. Prior abdominal surgery other than those that would not affect glucose metabolism, i.e., cholecystectomy, appendectomy, C-section or hysterectomy.
- iv. Pregnancy or active consideration of pregnancy during the period of study. Subjects will be discontinued if they become pregnant during the study.
- v. Hypersensitivity to liraglutide or any product components.
- vi. Personal or family history of medullary thyroid carcinoma or Multiple Endocrine Neoplasia type 2 in those who will undergo sleeve gastrectomy
- vii. Prior history of pancreatitis, cholelithiasis or cholecystitis.
- viii. Concurrent use of insulin or any other GLP-1 receptor agonist.
- ix. Active, severe psychiatric disease
- x. Pregnancy or breastfeeding

d) Surgery: Subjects will then undergo the surgery to which they had been assigned on clinical grounds. At present there are no clear guidelines in this regard and a patient is assigned to a bariatric surgical procedure based mainly on clinical factors. Clinical factors considered include the presence of specific obesity-related comorbid diseases and body mass index. Also considered are the patient's psychological complexity, social situation, and a patient's particular preference. A prior history of severe gastro-esophageal reflux is a relative contraindication to SG. **Note that the study team will play no role in that decision other than to ensure that participants in either group are matched for age, sex and BMI.** At Mayo Clinic, Rochester the standard protocol is to see patients back for care at 3, 6 and 12 months and then annually after bariatric surgery.

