e) Randomization: Subjects undergoing SG will be randomized (1:1) at the time of the 3 month visit after bariatric surgery. A double-blind design will be utilized. Liraglutide will be started at 0.6 mg SUBQ daily for 1 week. Subsequently, Liraglutide will be increased by 0.6 mg SUBQ daily on a weekly basis till the maintenance dose of 3.0 mg/day is reached. The placebo dose will also be titrated in a similar fashion. The study medication will be dispensed by the research pharmacy which will handle randomization and ensure that blinding is maintained. SG subjects will return to the CRTU for dispensing of study drug at standard follow-up visits (months 6, 12, 24, 36) and also at months 18 and 30. Subjects undergoing RYGB will return to the CRTU at standard follow up visits, months 3, 6, 12, 24, 36. Recruitment will continue till 50 subjects after SG are randomized and 25 subjects after RYGB are enrolled.

f) Study Visits: These will be timed to coincide with the standard follow-up visits at 3, 6, 12, 24 and 36 months after bariatric surgery. In addition to a history and physical examination, blood will be collected for creatinine, fasting glucose, HbA_{1c}, fasting lipid profile and hepatic panel, and urine collection to exclude pregnancy in females of child bearing potential. Supine and standing blood pressure will also be measured as well as body composition using DXA (at months 12, 24 and 36). Habitual activity levels⁴¹, bowel symptoms⁴², Stunkard's Eating Inventory⁴³, The Weight Efficacy Life-Style Questionnaire⁴⁴ & Eating and Weight Patterns-Revised⁴⁵ will be assessed. Collected data will include height, weight, blood pressure, pulse rate, medications used, and adverse events. During clinic visits, as per standard practice, subjects will meet with a dietitian and with a behavioral psychologist. Compliance will be assessed using an electronic record of food intake. The psychologist will use motivational enhancement and behavior change techniques to promote compliance with the dietary guidelines⁴⁷. In addition, to ensure compliance with instructions to increase physical activity, which will be reiterated at each visit, we will gather information about daily step counts from step-counters or smartphones.

g) Telephone follow up: The study coordinator will schedule monthly calls with each subject (or more frequently if necessary) to rapidly identify problems and help ensure compliance.

h) Early Termination

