compared to the SG + placebo group. Similarly, we will reject our 2° (i) hypothesis if the weight loss observed in participants who undergo SG and receive Liraglutide does not differ from that after RYGB. Such a conclusion would support a role of GLP-1 in the weight loss achieved (and maintained) after RYGB. The questionnaires collected over the duration of the study will be utilized to help generate hypotheses related to food intake as it is affected by liraglutide use after SG compared to placebo. As before, we will determine whether the addition of liraglutide to SG improves effects of SG on cholesterol and blood pressure ¹⁵. If this indeed the case, we will accept our 2° hypothesis (ii). If the high GLP-1 concentrations observed after RYGB modulate appetite and food intake as suggested by our preliminary data (Fig. 1), we would expect weight loss after RYGB to also lower cholesterol and blood pressure. We will reject our 2° (iii) hypothesis if the blood pressure and LDL-cholesterol lowering observed in participants who undergo SG and receive Liraglutide does not differ from that after RYGB.

STATISTICAL CONSIDERATIONS:

Using JMP® Pro 11.2.1 (SAS Institute) for the power calculation we established the following: -

In a prior experiment¹⁵ we observed an overall [mean value \pm (SD)] of % weight change after RYGB = $-26.1 \pm (8.7)$ at 1 year. Assuming similar variation, 25 subjects who complete the study in each group would provide approximately 80% power (at a 2-sided 0.05 α level), to detect a 7.0% difference in weight change between SG + treatment vs. SG + placebo. An intention to treat analysis will be undertaken.

In another, as yet unpublished experiment, 12 subjects studied before and 4 weeks after RYGB lost 11.0 ± 3.4 Kg within 4 weeks. Assuming similar variation, 25 subjects per group would provide approximately 80% power (at a 2-sided 0.05 α level), to detect a difference of a 2.7 Kg in weight between groups.

Schauer et al.¹⁴ observed an overall [mean value \pm (SD)] of weight change after RYGB = $-29.4 \pm (8.9)$ Kg. Assuming similar variation, 25 subjects per group would provide approximately 80% power (at a 2-sided 0.05 α level), to detect a 7.2kg between-group difference.

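### Secondary (i) and (iii) set SG + liraglutide against a non-randomised RYGB group; matching on age, sex and BMI does not ensure balance on starting blood pressure, LDL or their treatment, and no adjustment or caveat is planned

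*Combined protocol and SAP*

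**What the plan says.** Section e) Randomization limits randomisation to SG patients, 1:1, at the 3-month visit. RYGB patients form a concurrent group. Section d) Surgery says that the operation is assigned on clinical grounds: "Clinical factors considered include the presence of specific obesity-related comorbid diseases and body mass index". It also names psychological complexity, social situation and preference, and adds: "A prior history of severe gastro-esophageal reflux is a relative contraindication to SG". The study team has no part in the choice except to "ensure that participants in either group are matched for age, sex and BMI". No matching method or tolerance is given.

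The BMI criterion under a) Subjects admits patients at the lower BMI threshold "in the presence of at least one weight-related comorbid condition including hypertension, obstructive sleep apnea or dyslipidemia". The Baseline Visit includes a "history and physical examination including supine and standing blood pressure" and a fasting lipid profile.

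Secondary (i) states that SG + liraglutide gives less weight loss than RYGB. Secondary (iii) states that it "produces blood pressure and LDL-cholesterol lowering that is inferior to that achieved by RYGB". Under Interpretation, (iii) is rejected "if the blood pressure and LDL-cholesterol lowering observed in participants who undergo SG and receive Liraglutide does not differ from that after RYGB". For (i), the same finding of no difference is taken to support a role of GLP-1 in weight loss after RYGB. Statistical Considerations holds power calculations for weight and one sentence on intention to treat. It names no model or covariate.

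**The concern.** The outcomes of (iii) are blood pressure and LDL lowering. Patients who start higher usually have more room to fall, whether through treatment or through regression to the mean. If the choice of operation tracks hypertension or dyslipidemia, the two surgical groups may start at different levels. An unadjusted comparison of lowering could then show a difference that the operation and drug did not cause, or hide one that they did. Matching on age, sex and BMI is not aimed at these starting values or at antihypertensive and lipid-lowering treatment.

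For (i), matching on BMI deals with much of the obvious imbalance. The problem there is the conclusion. Reflux history, psychosocial factors and preference are unmatched, and any of them could move the contrast toward zero. As Interpretation is written, such a shift would count as evidence for a mechanism.

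**Working it through.** **Inputs from the documents:** 25 completers per group, two-sided 0.05, SD of % weight change 8.7, difference 7.0 points (stated for SG + treatment vs SG + placebo). **Assumed, because the documents give nothing:** SD of SBP change 15 mmHg, SD of baseline SBP 15 mmHg, slope of lowering on baseline 0.5 (range 0.3 to 0.7), and the size of any baseline gap.

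**1. The plan's own figure.** Noncentrality = 7.0 / (8.7 × √(2/25)) = 7.0 / 2.461 = 2.845. With 48 df the power is 79.6% (81.2% by the normal approximation), against a stated value of about 80%. It reproduces. It concerns the randomised SG comparison; no power is given for blood pressure or LDL.

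**2. (iii), unadjusted, no true difference.** Spurious shift = gap × slope = 4 × 0.5 = 2.0 mmHg. Standard error = 15 × √(2/25) = 4.243. Noncentrality = 2.0 / 4.243 = 0.471. The two-sided rejection rate is 7.5% instead of 5%.

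| Varying | Shift (mmHg) | False difference |
|---|---|---|
| slope 0.3 | 1.2 | 5.9% |
| slope 0.5 | 2.0 | 7.5% |
| slope 0.7 | 2.8 | 9.9% |
| slope 0.5, SD of change 12 | 2.0 | 8.9% |
| slope 0.5, SD of change 18 | 2.0 | 6.7% |

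If hypertensive and other patients differ by 20 mmHg (assumed), a 4 mmHg gap needs a 20-point difference in prevalence (20 × 0.20). Larger gaps are speculative: 10 mmHg would need 50 points (20 × 0.50).

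In SD units, which also serve for LDL, a gap of 0.25 SD with a baseline-to-follow-up correlation between 0.7 and 0.3 gives 6% to 8%.

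**3. (iii), ANCOVA on baseline, age, sex and BMI.** By simulation at slope 0.5 and a 4 mmHg gap, the false-difference rate returns to 5.1%.

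**4. When ANCOVA misleads.** If the slope is wholly regression to the mean, groups with different true levels do not differ in expected lowering, yet ANCOVA still subtracts slope × gap. At 4 mmHg that is an error of 0.5 × 4 = 2.0 mmHg, the size of the unadjusted error in step 2. At a speculative 10 mmHg the error is 5.0 mmHg, and the false-difference rate is 23% adjusted against 5% unadjusted. If half of the slope is regression to the mean, it is 7% adjusted against 12% unadjusted.

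**5. Precision for (iii).** Unadjusted 95% CI half-width = 2.011 × 4.243 = 8.5 mmHg. Adjusted, at slope 0.5, it is 7.8 (gap 4) or 8.1 (gap 10). If baseline does not predict change, it is 9.0 or 9.4.

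**6. (i).** Take 7.0 points as an assumed true RYGB advantage. With no confounding, the chance of finding no significant difference is 1 − 0.796 = 20%. With an assumed unmeasured shift of 3 points toward zero, noncentrality = 4.0 / 2.461 = 1.626 and that chance is 64%. Adjusting for three covariates unrelated to the shift leaves it at 66%.

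**The case against.** The strongest counter-argument is that the link to (iii) is inferred. Section d) does not say which comorbid diseases steer the choice and states that no clear guidelines exist. Hypertension and dyslipidemia are listed for eligibility for surgery, not for choice of procedure. Table 1, the only comorbidity-by-operation data, shows similar diabetes shares: 385/1419 = 27.1% for RYGB and 100/399 = 25.1% for SG. BMI matching also aligns comorbidity in part, because patients below the higher BMI threshold must have at least one such condition. Exclusion of diabetes, recent glucose-lowering drugs, severe psychiatric disease and active systemic or macrovascular disease narrows the groups further. All of this stands, and it limits the size that can be claimed. It does not close the point: diabetes is excluded from this trial, and its share says nothing direct about blood pressure or LDL.

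It is also fair to say that the protocol is open about clinical assignment, that it names no model for any endpoint, and that these are secondary comparisons. Randomisation protects the primary endpoint and (ii) from systematic baseline differences, however. Nothing does so for (i) and (iii).

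Finally, adjustment does nothing for (i), as step 6 shows. Part of the difficulty there is that failing to find a difference is weak evidence of similarity even without confounding. That is accepted, so the remedy for (i) concerns interpretation only.

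**Conclusion.** The point holds in a limited form. Secondary (i) and (iii) are observational contrasts, matching does not ensure balance on the variables that matter most for (iii), and the plan neither adjusts for them nor qualifies the mechanistic reading of (i). The plausible effect on (iii) is modest: about 8% instead of 5% for an assumed 4 mmHg gap, and roughly 6% to 10% over the slopes considered. Every blood pressure input is an assumption.

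A reader might infer that hypertensive or dyslipidemic patients are channelled to RYGB, so that (iii) is biased in a known direction. The documents support neither: they do not say which diseases lead to which operation, and they show no imbalance. A reader might also infer that adjustment would make the RYGB comparison causal, or that ANCOVA is always the safer estimate. Step 4 and the unmeasured selection factors rule out both. The primary endpoint and (ii) compare randomised groups and are not touched.

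**What to change.** 1. **(iii):** make ANCOVA on the pre-surgery value of the outcome (SBP or LDL), with age, sex and BMI, the main analysis. Report the unadjusted difference beside it as a sensitivity analysis, both with 95% CIs, and say why the two may disagree.
2. **Treatment:** add pre-surgery antihypertensive or lipid-lowering treatment as a covariate if the baseline history records it. Section f) Study Visits says "Collected data will include height, weight, blood pressure, pulse rate, medications used, and adverse events", but the Baseline Visit does not list medications. Confirm that they are captured before surgery, and do not substitute the post-surgery record. Report changes in these drugs during follow-up by group.
3. **(i):** no adjustment beyond the matching variables is needed. Report the difference with its 95% CI.
4. **Wording:** label (i) and (iii) as observational comparisons. State that confounding by comorbidity, reflux, psychosocial factors and preference remains. Amend Interpretation so that no difference in (i) is not by itself taken as support for a role of GLP-1.

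The cost is SAP text, one regression per outcome in (iii) and possibly one baseline medication field, with no extra patients or visits. Under the assumed inputs the half-width for SBP moves from 8.5 mmHg to between about 7.8 and 9.4. A treatment covariate that differs by group would widen it: 8.0 to 9.7 if used by 30% vs 50%. Unmeasured selection is not removed.

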For any patient enrolled in the study, the study participation will be concluded after the last visit at month 36, or at early termination. Should any patients withdraw or be withdrawn from the study, all of the Early Termination assessments should be completed before early termination, if possible, including; blood collection for creatinine, fasting glucose, HbA_{1c}, fasting lipid profile, hepatic panel, and urine collection to exclude pregnancy in females of childbearing potential. Supine and standing blood pressure will also be measured as well as body composition using DXA. Habitual activity levels, bowel symptoms, Stunkard's Eating Inventory, The Weight Efficacy Life-Style Questionnaire & Eating and Weight Patterns-Revised will be assessed. Collected data will include height, weight, blood pressure, pulse rate, medications used if applicable, and adverse events.

i) Power Calculation: See detailed power calculations below.

j) Adverse Event Monitoring: The most common adverse reactions associated with liraglutide use are nausea, dizziness, abdominal pain, increased lipase, hypoglycemia, diarrhea, constipation, vomiting, headache, decreased appetite and dyspepsia. Acute pancreatitis has been associated with liraglutide use. Relevant symptoms will be screened for at the time of routine follow-up as well as telephone follow-up.

1) Interpretation: We will accept our primary hypothesis that administration of 3.0mg liraglutide to participants after SG increases weight loss compared to placebo if after unblinding, the liraglutide group has significantly greater weight-loss from baseline

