In an experiment⁴⁷ where subjects were fed a diet similar to that consumed after bariatric surgery, we observed a weight change after 12 weeks of $-14.8 \pm (4.2)$ Kg. Assuming similar variation, 25 subjects per group would provide approximately 80% power (at a 2-sided 0.05 α level), to detect a 3.4kg between-group difference. Using % weight change, we observed a % change of $-14.0 \pm (3.0)$, giving us power to detect a 2.5% difference.

DATA HANDLING AND RECORD KEEPING:

The key personnel identified in this grant application have completed the required education on the protection of human research participants. The institution has established a formal program entitled the Mayo Investigator Training Program or MITP.

The MITP is a web based educational course designed to provide all personnel involved in human subject research with training about human subject protection. All Mayo personnel engaged in human subject research are required to complete the course. As detailed in the consent form, the **expected risks** include:

Blood sampling. Blood samples are collected by venipuncture for this study. Bruising can occur with venipuncture, as can fainting, etc. **Risk Monitoring / Risk Reduction:** The samples are collected using aseptic technique in designated venipuncture areas of the Clinic where facilities are available should untoward reactions (fainting, etc.) occur. Given the aseptic nature of the sample collection and the small risk of bruising, the monitoring plan is focused on advising volunteers to call the investigators should they have unusual pain or discomfort from the venipuncture site.

Radiation. Subjects will be exposed to radiation in this study. Lean body mass, percent body fat and visceral adiposity will be measured at the time of screening using DEXA (dual energy x-ray absorptiometry). **Risk Monitoring / Risk Reduction:** In all instances, the amount of radiation that a volunteer will receive will be well below levels that result in significant risk of harmful effects. Proposed radiation exposure will be reviewed by the Mayo Clinic Radiation Safety Board prior to initiation of any study. Women who could become pregnant will be required to have a negative pregnancy test prior to participation in each study utilizing radioactive tracers. The Mayo CRTU body composition core has a QDR4500 with fan scan technology which allows body composition to be performed in only a few minutes.

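### No urine pregnancy test is listed at the month 18 and month 30 study-drug dispensing visits, so scheduled tests are 12 months apart from month 12 to month 36

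*Combined protocol and SAP*

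**What the plan says.** Section f) Study Visits sets the timing of the assessment visits: "These will be timed to coincide with the standard follow-up visits at 3, 6, 12, 24 and 36 months after bariatric surgery". The assessments at those visits include "fasting lipid profile and hepatic panel, and urine collection to exclude pregnancy in females of child bearing potential".

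Section e) Randomization gives a longer list of visits for sleeve gastrectomy (SG) participants, who return for "dispensing of study drug at standard follow-up visits (months 6, 12, 24, 36) and also at months 18 and 30". No assessments are described for months 18 and 30.

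Pregnancy testing appears in three other places:

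- Section a) Subjects, at the baseline visit: "hepatic panel and urine collection to exclude pregnancy in females of child bearing potential".
- Section h) Early Termination, if possible: "urine collection to exclude pregnancy in females of childbearing potential".
- The Radiation paragraph under Data Handling and Record Keeping: "Women who could become pregnant will be required to have a negative pregnancy test prior to participation in each study utilizing radioactive tracers".

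The Study Schedule section only refers back to the study design.

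For the on-drug period, section e) states "Subjects undergoing SG will be randomized (1:1) at the time of the 3 month visit after bariatric surgery", and section h) states that "the study participation will be concluded after the last visit at month 36, or at early termination". No treatment duration is given in so many words.

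**The concern.** Exclusion criterion iv withdraws any participant who becomes pregnant, and inclusion criterion v requires contraception of women randomised to study drug who could conceive. The Pregnancy section requires follow-up of the pregnancy and reporting to the drug's manufacturer. Prompt action on these rules depends on prompt detection.

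The scheduled urine test is the only listed check that does not depend on what the participant says. The other routes are self-report (Pregnancy section), monthly coordinator calls (section g) and symptom screening (section j). No pregnancy question is specified for the calls or the screening. Symptoms are also a weak signal here, because the liraglutide reactions listed in section j) include nausea, vomiting and decreased appetite, which can also occur in early pregnancy.

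At months 18 and 30 more blinded drug is handed out without the test that accompanies dispensing at months 6, 12, 24 and 36. RYGB participants, who receive no study drug, have the same test schedule, so the spacing follows the clinic's routine follow-up rather than drug exposure. The issue is participant safety on study drug. It has no bearing on the endpoints, the power or the interpretation of the trial.

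**Working it through.** The plan gives no figure to reproduce on this point. The first step sets the two visit lists side by side.

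| Month after surgery | Study drug, SG (section e) | Urine pregnancy test (section f) |
|---|---|---|
| 3 | randomisation | yes |
| 6 | dispensing | yes |
| 12 | dispensing | yes |
| 18 | dispensing | **none listed** |
| 24 | dispensing | yes |
| 30 | dispensing | **none listed** |
| 36 | dispensing | yes |

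The radiation text does not fill the gap. It concerns tracer studies and, even if read to cover DXA, section f) places DXA at months 12, 24 and 36.

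**Intervals.** Tests at 3, 6, 12, 24 and 36 give gaps of 3, 6, 12 and 12 months. If the on-drug period runs from month 3 to month 36 (inferred), it lasts 33 months, and the 12-month gaps cover (12 + 12)/33 = 73% of it.

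**Wait to the next scheduled test.** Assume onset, meaning the first day a urine test would be positive, is uniform over a period T cut into intervals Lᵢ. The mean wait is ΣLᵢ²/(2T), and the share tested within d months is Σmin(Lᵢ, d)/T. For months 12 to 36, T = 24:

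| | As listed (12, 12) | With tests at 18 and 30 (6, 6, 6, 6) |
|---|---|---|
| Mean wait | (144 + 144)/48 = 6.0 months | (4 × 36)/48 = 3.0 months |
| Within 3 months | (3 + 3)/24 = 25% | (4 × 3)/24 = 50% |
| Within 6 months | (6 + 6)/24 = 50% | (4 × 6)/24 = 100% |

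Over all 33 months the mean wait falls from (9 + 36 + 144 + 144)/66 = 5.0 to (9 + 5 × 36)/66 = 2.9 months.

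**Expected events.** Section e) randomises 50 SG participants 1:1, so about 25 receive liraglutide. The documents give neither the share able to become pregnant nor a pregnancy rate on contraception. Assumed ranges are 25% to 75% and 1% to 5% per woman-year, over 2 years with everyone staying on drug:

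- Low: 25 × 0.25 × 2 × 0.01 = 0.125 pregnancies.
- High: 25 × 0.75 × 2 × 0.05 = 1.875 pregnancies.

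If 10% to 50% of these go unreported (also assumed), the range is 0.125 × 0.10 = 0.0125 to 1.875 × 0.50 = 0.94.

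**The case against.** The strongest reply is that the plan breaks no rule of its own. Section f) attaches the test to full study visits, not to dispensing, and nothing makes a negative test a condition of receiving drug. Months 18 and 30 can be read as deliberate light pick-up visits. This is correct. The standard applied here is only the plan's practice at its other named dispensing visits, and no rationale is given for the two exceptions.

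Second, Study Drugs and Materials says dispensed drug is used within 30 days. If that implied monthly resupply, most dispensing would be untested and the count of four tested visits out of six would not describe practice. The sentence reads more naturally as an in-use limit. On either reading, months 18 and 30 have no listed test and the 12-month gaps remain.

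Third, existing safeguards are substantial: women actively considering pregnancy are excluded, contraception is required, pregnancy must be reported at once, and calls are monthly. These lower the number of undetected pregnancies, but none is an objective test. The withdrawal rule also covers RYGB participants, so it is not specific to drug exposure, and the documents give no fetal risk figure for liraglutide.

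Fourth, the event estimate multiplies three assumed ranges and spans 0.94/0.0125 = 75-fold. That stands. So does the point that a mean wait of 6.0 months overstates undetected exposure: 3/12 = 25% of onsets would wait more than 9 months, beyond the end of the pregnancy. Capping waits at an assumed 9 months gives (9²/2 + 3 × 9)/12 = 5.6 months as listed. The 3.0 months after the change is unaffected, since no wait then exceeds 6 months.

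Finally, even with the change, half of onsets have no scheduled test within 3 months, so early detection still rests mainly on self-report and calls.

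**Conclusion.** The concern holds. The schedule facts are certain from sections e) and f): no test is listed at two of six return dispensing visits, and scheduled tests are 12 months apart in months 12 to 24 and 24 to 36. The halving of the longest interval follows directly. The mean-wait and share figures rest on uniform onset, and apply only to a pregnancy not already reported by the participant or found on a call. The expected number of such pregnancies is small, about 0.01 to 0.9 in the liraglutide arm, and depends wholly on the assumed ranges. This is a modest safety improvement that should be made because it is very cheap; it is not a defect that threatens the trial.

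**What to change.** Add one sentence to section e) or f): at the month 18 and month 30 dispensing visits, do the section f) urine pregnancy test in women who could become pregnant before study drug is handed out. No other change is proposed.

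The cost is at most two urine tests per SG participant: 2 × 50 = 100 for the 50 randomised under section e), or 2 × 60 = 120 if the 60 proposed at the start of the design section are all randomised. At an assumed 25% to 75% share of eligible women among 50, it is 2 × 50 × 0.25 = 25 to 2 × 50 × 0.75 = 75 tests. Participants already attend these visits, so no extra visit or new type of procedure is needed.
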